10.	Lens Fit Assessment	
The general lens fit characteristics will be recorded for both study lenses. These include lens position (centration, limbal exposure, edge lift), and movement (primary and up gaze as well as push-up).
 
Fit acceptability is defined as:
 
 • No limbal exposure (presence of clear cornea) in primary gaze or with extreme eye movements. • No edge lift • No insufficient/excessive, unacceptable movement in all three movement assessments (Primary Gaze, Upgaze and Josephson Push-up). If lens movement is insufficient and unacceptable in primary gaze and upgaze but is acceptable with the Josephson Push-up technique, the fit will be deemed acceptable. 
*Note: If the lens fit is deemed unacceptable, discontinue the subject and proceed to final evaluation.
	
11.	Lens Deposits	
Front and Back Surface Lens Deposits Back Trapped Debris and Mucin Plugs Lens damage (draw and describe)
	
12.	Lens Wettability	Subjective Lens Surface Wettability	
13.	Conjunctival Hyperemia	Record Limbal and Bulbar Conjunctival Hyperemia findings	
14.	Lens Removal	
The subject will remove lenses. Lenses will be saved in lens case with Revitalens OcuTec®
 
Note: Subject should not rub lenses.
	
15.	Biomicroscopy	
Slit Lamp Classification Scale ([REDACTED] will be used to grade the findings. The following [REDACTED] will be used to assess specific ocular physiology in greater detail: (0.50 steps)
 
 • [REDACTED] : Corneal staining • [REDACTED] : Conjunctival staining 
Note: Subject must be free of any FDA grade 3 or greater slit lamp findings with no active ocular infection/inflammation.
	
16.	Eye Rinse	The investigator or clinical staff will rinse the subject's eyes thoroughly with unpreserved saline.	
17.	Lens Insertion	Subjects will remove the lenses from the lens case and re-insert the lenses.	
18.	Visual Acuity	Record the distance Snellen visual acuity with their study lenses correction in place for OD, OS, OU. Subject must keep reading smaller lines until less than half of the letters are correctly identified. Subject must be 20/30 or better OD and OS to continue.	
19.	Follow-up visit scheduling	An appointment for the next visit should be made for approximately 1 week (6 to 9 days) after the follow-up visit. Subjects should be advised to wear the study lenses eight hours each day and to the follow-up visit, after a minimum of 8 hours wear that day .	

Visit 4: Subjects must present to Visit 4 having worn the study lenses for at least 8 hours.

VISIT 4: TREATMENT 1- FOLLOW-UP 3 (3-WEEK)		
Step	Descriptor	Details
1.	Concomitant Medication and Medical History Review	Record any changes in concomitant medications or health status since the last visit.
2.	Contact lens wear times	Record the current wear time (WT) and comfortable wear time (CWT).
3.	Compliance	Record the subject's compliance with wearing the study lenses. Note whether the subject chose to rub the lenses clean after use.
4.	Subject-reported Ocular Symptoms	Record Subject Reported Ocular Symptoms or Problems
5.	CLUE Questionnaire	Subject will complete the Contact Lens User Experience questionnaire regarding their experiences with the study lenses.
6.	GSI Questionnaire	Subject will complete GSI questions regarding their experiences with the study lenses.
7.	Distance visual acuity	Record the distance Snellen visual acuity for OD, OS, OU. Subject must keep reading smaller lines until less than half the letters are correctly identified
8.	Toric Fit Evaluation	
Record:
 
 • The rotational position to the nearest degree • Lens stability with blink • Lens stability with eye versions • Toric fit acceptable or unacceptable 
Toric lens fit will be unacceptable if lenses rotated more than 20 degrees, or lens stability is worse than 5 degrees movement with blink. If toric fit is unacceptable, proceed to final evaluation.

9.	Lens Fit Assessment	
The general lens fit characteristics will be recorded for both study lenses. These include lens position (centration, limbal exposure, edge lift), and movement (primary and up gaze as well as push-up).
 
Fit acceptability is defined as:
 
 • No limbal exposure (presence of clear cornea) in primary gaze or with extreme eye movements. • No edge lift • No insufficient/excessive, unacceptable movement in all three movement assessments (Primary Gaze, Upgaze and Josephson Push-up). If lens movement is insufficient and unacceptable in primary gaze and upgaze but is acceptable with the Josephson Push-up technique, the fit will be deemed acceptable. 
*Note: If the lens fit is deemed unacceptable, discontinue the subject and proceed to final evaluation.

10.	Lens Deposits	Front and Back Surface Lens Deposits Back Trapped Debris and Mucin Plugs Lens damage (draw and describe)

11.	Lens Wettability	Subjective Lens Surface Wettability	[REDACTED]
12.	Conjunctival Hyperemia	Record Limbal and Bulbar Conjunctival Hyperemia findings	[REDACTED]
13.	Lens Removal	The subject will remove lenses. Lenses will be saved in lens case with Revitalens OcuTec® Note: Subject should not rub lenses.	
14.	Biomicroscopy	Slit Lamp Classification Scale ([REDACTED] will be used to grade the findings. The following [REDACTED] will be used to assess specific ocular physiology in greater detail: (0.50 steps) 
 • [REDACTED] : Corneal staining • [REDACTED] : Conjunctival staining Note: Subject must be free of any FDA grade 3 or greater slit lamp findings with no active ocular infection/inflammation.	[REDACTED] [REDACTED] [REDACTED]
15.	Eye Rinse	The investigator or clinical staff will rinse the subject's eyes thoroughly with unpreserved saline.	
16.	Lens Insertion	Subjects will remove the lenses from the lens case and re-insert the lenses.	
17.	Visual Acuity	Record the distance Snellen visual acuity with their study lenses correction in place for OD, OS, OU. Subject must keep reading smaller lines until less than half of the letters are correctly identified. Subject must be 20/30 or better OD and OS to continue.	[REDACTED]
18.	Follow-up visit scheduling	An appointment for the next visit should be made for approximately 1 week (6 to 9 days) after the follow-up visit. Subjects should be advised to wear the study lenses eight hours each day and to the follow-up visit, after a minimum of 8 hours wear that day.	

Visit 5: Subjects must present to Visit 5 having worn the study lenses for at least 8 hours.

VISIT 5: TREATMENT 1- FOLLOW-UP 4 (4-WEEK)			
Step	Descriptor	Details	or Appendix
1.	Concomitant Medication and Medical History Review	Record any changes in concomitant medications or health status since the last visit.	
2.	Contact lens wear times	Record the current wear time (WT) and comfortable wear time (CWT).	
3.	Compliance	Record the subject's compliance with wearing the study lenses. Note whether the subject chose to rub the lenses clean after use.	
4.	Subject-reported Ocular Symptoms	Record Subject Reported Ocular Symptoms or Problems	[REDACTED]
5.	CLUE Questionnaire	Subject will complete the Contact Lens User Experience questionnaire regarding their experiences with the study lenses.	
6.	GSI Questionnaire	Subject will complete GSI questions regarding their experiences with the study lenses.	
7.	Distance visual acuity	Record the distance Snellen visual acuity for OD, OS, OU. Subject must keep reading smaller lines until less than half the letters are correctly identified	[REDACTED]
8.	ETDRS Visual performance	Under high illumination and high chart luminance record the distance high contrast visual acuity for OD, OS, OU using ETDRS charts at 4 meters.	[REDACTED]
9.	Spherical Over-refraction	Record the spherical over-refraction OD and OS. Record the distance visual acuity with the contact lenses (OD, OS) to the nearest letter.	
10.	Toric Fit Evaluation	
Record:
 
 • The rotational position to the nearest degree • Lens stability with blink • Lens stability with eye versions • Toric fit acceptable or unacceptable 
Toric lens fit will be unacceptable if lenses rotated more than 20 degrees, or lens stability is worse than 5 degrees movement with blink. If toric fit is unacceptable, proceed to final evaluation.
	[REDACTED]

11.	Lens Fit Assessment	
The general lens fit characteristics will be recorded for both study lenses. These include lens position (centration, limbal exposure, edge lift), and movement (primary and up gaze as well as push-up).
 
Fit acceptability is defined as:
 
 • No limbal exposure (presence of clear cornea) in primary gaze or with extreme eye movements. • No edge lift • No insufficient/excessive, unacceptable movement in all three movement assessments (Primary Gaze, Upgaze and Josephson Push-up). If lens movement is insufficient and unacceptable in primary gaze and upgaze but is acceptable with the Josephson Push-up technique, the fit will be deemed acceptable. 
*Note: If the lens fit is deemed unacceptable, discontinue the subject and proceed to final evaluation..
	
12.	Lens Deposits	
Front and Back Surface Lens Deposits Back Trapped Debris and Mucin Plugs Lens damage (draw and describe)
	
13.	Lens Wettability	Subjective Lens Surface Wettability	
14.	Conjunctival Hyperemia	Record Limbal and Bulbar Conjunctival Hyperemia findings	
15.	Lens Removal	
All lenses will be retained. Upon removal of the lenses (without gloves), the investigator or clinical staff will store lenses in a clean vial with non- preserved saline with a label detailing the study number, subject number, subject global ID, date, lens type, eye the lens was worn on, and time of lens wear (in days). All lenses will be stored in the refrigerator.
	
16.	Biomicroscopy	
Slit Lamp Classification Scale ([REDACTED] will be used to grade the findings. The following [REDACTED] will be used to assess specific ocular physiology in greater detail: (0.50 steps)
 
 • [REDACTED] : Corneal staining • [REDACTED] : Conjunctival staining 
Note: Subject must be free of any FDA grade 3 or greater slit lamp findings with no active ocular infection/inflammation.
	
17	Eye Rinse	The investigator or clinical staff will rinse the subject's eyes thoroughly with unpreserved saline.	

Final Evaluation: The final evaluation will ordinarily take place after Visit 5 completed. It may also take place at any point the subject discontinues the study or is terminated from the study.

FINAL EVALUATION			
Step	Descriptor	Details	or Appendix
1	Final Exam Form	Indicate if the subject completed the study successfully or not. If subject discontinued, indicate the reason.	
2	Best-corrected Distance Visual Acuity	Record the subject's best corrected distance visual acuity with refraction OD, OS, and OU.	
3	Investigator Signature	Investigator must review and sign the eCRF.	

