4.4.1 TIME AND EVENT SCHEDULE

Event	Visit 1 Day 0 (Consent, Baseline, Study Lens Dispense)	Visit 2 6-9 days after Visit 1 (Study Lens Follow-Up)	Visit 3 6-9 days after Visit 2 (Study Lens Follow-Up)	Visit 4 6-9 days after Visit 3 (Study Lens Follow-Up)	Visit 5 6-9 days after Visit 4 (Study Lens Follow-Up; Final Evaluation)
Study Informed Consent	X				
Demographics	X				
Medical History	X	X	X	X	X
Contact Lens History	X				
Inclusion/Exclusion Criteria	X				
PRO Questionnaire	X	X	X	X	X
Ocular Symptoms	X	X	X	X	X
Subjective Refraction	X				
Slit Lamp Findings	X	X	X	X	X
Lens (test article) Fitting	X				
Spherical Over-Refraction	X				X
Snellen Visual Acuity	X	X	X	X	X
Visual Performance (ETDRS)	X		X		X
Lens Fit Assessment	X	X	X	X	X
Lens Surface Evaluation	X	X	X	X	X
Lens Wettability	X	X	X	X	X
Lens Removal		X	X	X	X
Lens Insertion	X	X	X	X	
Dispense Lens	X				
Compliance / Wear Time		X	X	X	X
Final Evaluation Form					X
Adverse Event Review	X	X	X	X	X
Concomitant Medication Review	X	X	X	X	X
Study Completion					X

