6.	Biomicroscopy	
Slit Lamp Classification Scale (2018) will be used to grade the findings.
 
The following [REDACTED] will be used to assess specific ocular physiology in greater detail: (0.50 steps)
 
 [REDACTED] : Limbal and conjunctival redness [REDACTED] : Corneal staining [REDACTED] : Conjunctival staining 	
7	Eligibility after Baseline Examination	All responses to Inclusion Criteria questions must be answered “yes,” and all responses to Exclusion Criteria questions must be answered “no” for the subject to be considered eligible.	

VISIT 1: TREATMENT 1 - ASSIGNMENT 1			
Step	Descriptor	Details	or Appendix
1.	Lens Information	
Select lens type based on Randomization scheme
 
Select the lens powers based on the following guide:
 
 • The cylinder & axis are as close as possible to the vertex corrected refraction • Do not over-correct cylinder power • The best spherical equivalent of the toric contact lens should be as close as possible to the spherical equivalent (SE) of the subject's vertexed refraction 
For example :
 
Subject's refraction: -2.00-1.00 x180 (SE -2.50DS)
 
Lens choice A: -2.00-0.75 x 180 (SE -2.37)
 
Lens choice B: -2.25-0.75x180 (SE -2.62)
 
Lens choice A should be chosen in this example
	

Step		Descriptor	Details	or Appendix
1.		Right Lens Insertion	
The investigator or subject will place the lens on eye. If the lens is uncomfortable, inspect for damage and remove, reinsert or replace as necessary. If lens damage is present, complete the Product Quality Complaint Form and return the lens to the Sponsor. The lens will be stored in labeled vial with unpreserved saline, and clearly differentiated from the other worn lenses that will be shipped back to the Sponsor.
	
2.		Timed settling for right lens	
The investigator will start a stopwatch or timer as soon as the right lens is inserted.
 
Note: Study lenses have scribe marks at either 6 o'clock and 12 o'clock positions or 3, 6, 9 o'clock positions. Rotation measurements are made relative to a vertical reference line. Record base nasal or base temporal to the nearest degree.
 
At one (1) minute after insertion: Record the rotational position to the nearest degree
 
At three (3) minutes after insertion: Record the rotational position to the nearest degree
	

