9.	Lens Fit Assessment	
The general lens fit characteristics will be recorded for both study lenses. These include lens position (centration, limbal exposure, edge lift), and movement (primary and up gaze as well as push-up).
 
Fit acceptability is defined as:
 
 • No limbal exposure (presence of clear cornea) in primary gaze or with extreme eye movements. • No edge lift • No insufficient/excessive, unacceptable movement in all three movement assessments (Primary Gaze, Upgaze and Josephson Push-up). If lens movement is insufficient and unacceptable in primary gaze and upgaze but is acceptable with the Josephson Push-up technique, the fit will be deemed acceptable. 
*Note: If the lens fit is deemed unacceptable, discontinue the subject and proceed to final evaluation

10.	Lens Deposits	Front and Back Surface Lens Deposits Back Trapped Debris and Mucin Plugs Lens damage (draw and describe)	[REDACTED] [REDACTED]
11.	Lens Wettability	Subjective Lens Surface Wettability	[REDACTED]
12.	Conjunctival Hyperemia	Record Limbal and Bulbar Conjunctival Hyperemia findings	[REDACTED]
13.	Lens Removal	The subject will remove lenses. Lenses will be saved in lens case with Revitalens OcuTec® Note: Subject should not rub lenses.	
14.	Biomicroscopy	Slit Lamp Classification Scale ([REDACTED] will be used to grade the findings. The following CTP's will be used to assess specific ocular physiology in greater detail: (0.50 steps) 
 • [REDACTED] : Corneal staining • [REDACTED] : Conjunctival staining Note: Subject must be free of any FDA grade 3 or greater slit lamp findings with no active ocular infection/inflammation.	[REDACTED] [REDACTED] [REDACTED]
15.	Eye Rinse	The investigator or clinical staff will rinse the subject's eyes thoroughly with unpreserved saline.	
16.	Lens Insertion	Subjects will remove the lenses from the lens case and re-insert the lenses.	
17.	Visual Acuity	Record the distance Snellen visual acuity with their study lenses correction in place for OD, OS, OU. Subject must keep reading smaller lines until less than half of the letters are correctly identified. Subject must be 20/30 or better OD and OS to continue.	[REDACTED]

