5.1 WITHDRAWAL CRITERIA

A subject will be withdrawn from the study for any of the following reasons:

- Lost to follow-up
- Withdrawal of consent
- Death
- Discontinuation of study treatment as a result of the investigator's clinical judgment that for safety reasons (e.g., adverse event) it is in the best interest of the subject to stop treatment.
- The subject becomes pregnant.

For discontinued subjects, the Investigator will:

- Update the enrollment log to document reason for discontinuation
- Complete the "last" Follow-up Visit form (scheduled or unscheduled)
- Complete the Final Evaluation form, indicating the reason that the subject was discontinued from the study
- Record the spherocylindrical refraction with best corrected distance visual acuity
- Collect used study lenses and test articles (worn or brought to the visit) from the subject and discard them
- Collect all unused study lenses and test articles from the subject

Subjects becoming pregnant during the study will be discontinued. Once discontinued, pregnant participants and their fetuses will not be monitored for study related purposes. At the Investigators' discretion, the study participant may be followed by the Investigator through delivery. However, this data will not be collected as part of the clinical study database. Pregnant participants are not discontinued from contact lens or solution related studies for safety concerns, but due to general concerns relating to pregnancy and contact lens use. Specifically, pregnant women are discontinued due to fluctuations in refractive error and/or visual acuity that occur secondary to systemic hormonal changes, and not due to unforeseen health risks to the mother or fetus.

In cases where a subject is lost to follow-up, every possible effort must be made to contact the subject and determine the reason for discontinuation / withdrawal. The measures taken to follow up must be documented including two written attempts and a certified letter as the final attempt.

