9.7 EVALUABLE SUBJECTS

Accountability (disposition) of all enrolled subjects will be presented in each of the following status subgroups.

1. Completed: Randomized subjects who are eligible to participate in the study and have successfully completed all required visits including the final visit.
2. Discontinued: Randomized subjects who are prematurely discontinued from the study due to any reasons described in Section 5.1.
3. Total Dispensed: Subjects who administered the test article at least once (i.e. Lens insertion occurred in at least one eye).
4. Enrolled Not Dispensed: Subjects who were (i) enrolled in the study (provided informed consent) but failed to satisfy the eligibility criteria (inclusion/exclusion criteria), (ii) randomized but discontinued or drop out prior to administering the test article, or (iii) not randomized to treatment for any reason.
5. Total enrolled: Subjects who signed the informed consent form (i.e. completed + discontinued + Enrolled not dispensed).

Subjects will be allocated to the following study populations for the analysis purpose.

1. Safety Population: All subjects who are administered the test articles and have at least one observation on any safety or/and efficacy variables.
2. Per-protocol Population: All subjects who have successfully completed all required visits without any major protocol deviations that the cohort review committee documents as impacting the assessment of the hypotheses prior to the data hard-lock.

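### Fit stop rules at Visits 2-5 precede the slit-lamp exam and leave it unclear whether corneal staining is still graded; at Visit 5 the stop protects no one

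*Protocol*

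**What the plan says.** Protocol 4.7.1 has two fit stops at each of Visits 2 to 5. The toric-fit step says "If toric fit is unacceptable, proceed to final evaluation". The next step, lens fit, says "If the lens fit is deemed unacceptable, discontinue the subject and proceed to final evaluation". Lens removal, biomicroscopy (which includes the corneal staining grade) and eye rinse come later in the same visit. The biomicroscopy step is also a safety check: "Subject must be free of any FDA grade 3 or greater slit lamp findings".

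The final evaluation has three items: a form recording whether the subject completed or discontinued, best-corrected acuity with refraction, and the investigator's signature. On timing, "The final evaluation will ordinarily take place after Visit 5 completed"; it may also happen whenever a subject discontinues or is terminated.

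Other provisions bear on the point:
- Protocol 4.4.1 marks slit-lamp findings at all five visits.
- Protocol 5.1 has the investigator complete the last follow-up visit form for discontinued subjects.
- Protocol 6.3 requires the final study visit forms when the investigator withdraws a subject, and makes slit-lamp findings a minimum item at unscheduled visits.
- Protocol 9.7 defines Discontinued as "Randomized subjects who are prematurely discontinued from the study due to any reasons described in Section 5.1". SAP 4.2 does the same.
- SAP 2.3.1 limits the efficacy set, used for all secondary endpoints, to subjects who completed every required visit.
- SAP 5.2.2 judges staining over all planned and unscheduled visits. SAP 5 places the primary analyses on the safety set, and SAP 5.1.2 rules out imputation.

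**The concern.** Followed in step order, a fit stop takes the subject past that visit's slit-lamp exam. The grade at risk belongs to an eye whose lens has just failed a fit check. The documents do not link fit to staining. If poor fit does raise staining, missed grades would understate the rate for whichever lens has more fit failures.

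At Visits 2 to 4 it is sensible to stop further wear. At Visit 5 no lens is re-inserted or dispensed and the final evaluation follows anyway, so the stop has nothing to prevent. It can still do two things: omit the exit staining grade, and lead a site to record as discontinued someone who attended every visit. By then the questionnaires and acuity measures have been collected at earlier Visit 5 steps. The efficacy set would lose complete CLUE and Visit 1 acuity data for a reason related to lens performance.

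Lens fit, rotation and blink stability are primary endpoints only at Visit 1 and are not affected.

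**Working it through.** **Step order (Protocol 4.7.1).** The last column assumes that the exam is skipped at the visit where the stop occurs.

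| Visit | Fit stops | Lens removal | Biomicroscopy | Eye rinse | On-lens planned grades left, of those due |
|---|---|---|---|---|---|
| 2 | 8-9 | 13 | 14 | 15 | 0 of 1 |
| 3 | 9-10 | 14 | 15 | 16 | 1 of 2 |
| 4 | 8-9 | 13 | 14 | 15 | 2 of 3 |
| 5 | 10-11 | 15 | 16 | 17 | 3 of 4 |

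For a stop at visit v, v − 1 on-lens grades are due and v − 2 remain. Visit 1 contributes none: its slit-lamp exam is baseline step 6, followed by "Eligibility after Baseline Examination" and only then by insertion of the study lens. Visit 2 is therefore the worst case, with no on-lens grade from a planned visit.

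**Status at Visit 5.** Step 10 does not use the word discontinue; step 11 does. Protocol 9.7 requires a premature exit for a Section 5.1 reason. An unacceptable fit is not named in 5.1, and someone at the last visit has not left early. Section 9.7 thus points to Completed while step 11 says the opposite, and the final evaluation form makes the site choose.

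**Number of subjects.** The plan gives no figure to reproduce and no fit failure rate at follow-up. Assume a rate q per subject per visit, constant and independent across visits, with n = 135 per arm (SAP 1.5).
- Stopped at Visit 5, if all reach it: n × q. At q = 1%, 135 × 0.01 = 1.35; at q = 5%, 6.75.
- Stopped at any of Visits 2-5: n × (1 − (1 − q)^4). At q = 1%, 135 × (1 − 0.99^4) = 5.3; at q = 5%, 135 × (1 − 0.95^4) = 25.0.
- At q = 0, both are zero.

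The low end is more plausible. Historical acceptable fit and blink stability were both 100% at fitting (SAP 1.5), and subjects with an unacceptable fit already leave at Visit 1.

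**Grade 3 or higher eyes missed, per arm.** Eyes stopped × event rate, if every stop skips the exam:
- At the plan's rate of 0.005% (0.00005): q = 1% gives 2 × 5.3 × 0.00005 = 0.0005; q = 5% gives 2 × 25.0 × 0.00005 = 0.0025.
- If 0.005 was meant as a proportion (an assumption): 2 × 5.3 × 0.005 = 0.05, and 2 × 25.0 × 0.005 = 0.25.

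These figures treat fit and staining as unrelated. They are generous in that the rate covers the whole wear period while a stop loses one visit. They would be too low if poor fit raises staining.

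**Effect of one event on the staining result.** SAP 5.2.2 concludes no difference if the 95% CI of the odds ratio contains 1. As a rough stand-in, Fisher's exact test with 270 eyes per arm, treated as independent, gives p = 1.00 for 1 v 0, p = 0.061 for 5 v 0 and p = 0.030 for 6 v 0. Starting from no events, one recovered grade would not alter the conclusion.

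**The case against.** The strongest reply is that no site would follow the steps literally. Going straight from the fit step to the final evaluation also skips lens removal, yet the final evaluation needs a best-corrected refraction, so the lenses must come off. Sections 5.1 and 6.3, the event schedule and the normal timing of the final evaluation all favour finishing the visit. At Visits 2 to 4 an early final evaluation is provided for only when a subject discontinues or is terminated, so even the toric-fit stop reads as a discontinuation and brings in Section 5.1. On status, 9.7 favours Completed, 5.1 does cover stopping on clinical judgment for safety, and the cohort committee reviews every deviation.

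Most of this stands. A reader might infer that the protocol tells sites to omit the staining exam. The documents do not support that: they give instructions that are not reconciled, and the fuller visit is the likelier intention. A reader might also infer that an ungraded eye would be scored as acceptable. SAP 5.1.2, which bars imputation and reports counts of non-missing values, largely answers that.

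What remains is narrower. Completing a form is not the same as performing a bypassed procedure, and no visible sentence requires the exam. The staining, fit, toric-fit and biomicroscopy appendices appear only as titles, so this can be said only of the visible text. The committee classifies deviations; it is given no stated role in changing a subject recorded as discontinued.

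**Conclusion.** The point holds as a minor conflict of instructions on a co-primary safety endpoint, together with a purposeless stop at Visit 5 that can cause a fit-related exclusion from the efficacy set. The step order and the content of the final evaluation are plain from the text. How often the stop would occur, and how sites would read it, are not known.

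It would go too far to say that the staining comparison or the secondary tests are biased. Few subjects are likely to be affected. Under the assumed failure rates of 0% to 5% per visit, expected missed grade 3 or higher eyes are 0 to 0.0025 per arm at the plan's rate, or 0 to 0.25 at the higher assumed rate. No change in any primary or secondary conclusion has been shown, and sample size and type I error are untouched. The case for acting is that the correction is free and secures a slit-lamp exam in an eye with a poorly fitting lens.

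**What to change.** **Visit 5, steps 10-11:** replace the stop wording with an instruction to record the result and complete all remaining steps (through step 17) before the final evaluation.

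**Visits 2-4, toric-fit and lens-fit steps:** keep the stop on further wear, but require lens removal without re-insertion, biomicroscopy with the staining grade, and eye rinse before the final evaluation.

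**Protocol 9.7 and SAP 2.3.1/4.2:** add a sentence that a subject whose unacceptable fit is first recorded at Visit 5 counts as Completed and is not excluded from the efficacy set for that reason.

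The cost is wording in the fit steps of four visits and one sentence in each document's definitions. The slit-lamp exam is already scheduled at each of these visits, so no procedure is added. No addition to SAP 5.2.2 is needed.
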